12.2 Screening Period Procedures

Written informed consent must be obtained before performing any study specific medical procedures. The screening visit will take place at study days -28 to zero. All patients must take part in the informed consent process. During the consent process, the person obtaining consent must inform the patient of all elements of informed consent. Adequate time must be allowed for the patient to make questions and to make a voluntary decision. No protocol-specific procedures are to be performed until the patient has signed and dated an informed consent form (IC) approved by an Ethics Committee for investigation with medicinal products (CEIm). Each patient's participation in the trial begins with the signing and dating of the informed consent form.

During the screening visit, inclusion and exclusion criteria will be assessed.

For details of assessments required during screening, please refer to Tables 14 and 16.

The screening RT-qPCR blood sample will be analyzed by a Sponsor designated central laboratory. In case the BCR-ABL1 status cannot be determined on this sample (e.g., due to technical or logistical issues) another blood sample for RT-qPCR is to be collected immediately and submitted to the central laboratory for determination of the BCR-ABL1 status.

Laboratory baseline assessments (including hematology and chemistry), physical examination including performance status, height, weight, ECG and vital signs must be performed within 28 days prior to Cycle 1/study Day 1, before the first IMP dose. As long as a patient that has signed the IC fulfill all inclusion criteria and none of the exclusion criteria, he/she could be included in this study.

12.3 Eligibility Screening

The investigator will send the eligibility check form to the Sponsor by email ([contact]). The investigator will be allowed to assign treatment to the patient if he/she fulfills all inclusion criteria and none exclusion criteria.

12.4 Information to Be Collected on Screening Failures

Patients who sign the study informed consent but fail to start the treatment for any reason will be considered a screen failure. The reason(s) for not starting the treatment will be recorded on the source document and the CRF. The demographic information, informed consent, and Inclusion/Exclusion pages must also be completed for Screening Failure patients, if it is possible. No other data will be entered into the CRF for those subjects who are screen failures.

12.5 Medical/Surgical History and Demographics

Medical and surgical history and demographic information will be recorded. Medical and surgical history includes diagnoses, therapies, and medical and surgical treatments.

Demographic information consists of the patient's age, gender, and race.

12.6 Recent Medication Prior to First IMP Dose

The relevant medication at the time of the IC signature will be obtained from each patient at the time of screening and before the first IMP dose. It will be recorded in the CRF.

12.7 Leukemia Diagnosis and Prior Cancer Therapy

Both the initial leukemia diagnosis and the current screening diagnosis must be recorded. Note: Only patients currently in CP-CLM and those with no prior history of CML-AP, or CML-BC, or stem cell transplant are eligible.

12.8 Sokal Risk Score

Sokal risk score will be collected at screening. Risk category based on Sokal score is calculated using the following formula based on parameters from time of diagnosis:

Table 18: Sokal Formulation

Sokal Variables (from Sokal et al, 1984)	
Age (years)	0.0116 (age - 43.4)
* Spleen (cm)	0.0345 (spleen - 7.51)
Platelets ($\times 10^9/L$)	0.188 $[(platelets/700)^2 - 0.563]$
^ Blasts (%)	0.0887 (blasts - 2.10)
Relative Risk (RR)	Exponential of the total
* Maximum distance from costal region	
^ Percent in peripheral blood	

In the Sokal formulation, all four variables are continuous.

- Low risk patients have a Relative Risk (RR) < 0.8
- Intermediate risk patients have a RR ≥ 0.8 and ≤ 1.2
- High risk patients have a RR > 1.2

12.9 Vital Signs

Vital signs are temperature, pulse, respiratory rate, and blood pressure (when the patient is seated). The vital signs must be performed before treatment at the following visits:

- Screening
- During first therapy:
 - Day 1 of cycle 1 (before treatment).
 - Day 15 of cycle 1
- During second therapy (before treatment):

- Day 1 of cycle 2. Before the patient takes the bosutinib plus atezolizumab combination for first time.
- The vital signs test should also be performed on days 15 of cycles 2 and 3, only for the first group of patients.
- Day 1 of cycles 3, 4, 5, 6, 7, 8, 9, 10, 11, 12 and 13.
- During third therapy:
 - Day 1 of cycle 14. Before the patient takes bosutinib 400 mg/day in monotherapy, for the first time again for the treatment of CML.
 - Day 1 of cycles 17, 20 and 23.
 - At the End of Treatment: Day 29 (Last dose) of cycle 25.
 - At the End of Study, (visit EOS or follow up): 28 days after the last dose.

12.10 Height and Weight

Height in centimeters (cm) and body weight in Kg (reported to the first decimal) (in indoor clothing, but without shoes) will be measured.

Height measurement is required at screening only.

Weight will be measured at:

- Screening
- During first therapy (before treatment):
 - Day 1 of cycle 1.
- During second therapy (before treatment):
 - Day 1 of cycle 2. Before the patient takes the bosutinib plus atezolizumab combination for first time.
 - Day 1 of cycles 4, 7, 10, and 13.
- During third therapy:
 - Day 1 of cycle 14. Before the patient takes bosutinib 400 mg/day in monotherapy, for the first time again for the treatment of CML.
 - Day 1 of cycles 17, 20 and 23.
 - At the End of Treatment: Day 29 (Last dose) of cycle 25.
 - At the End of Study, (visit EOS or follow up): 28 days after the last dose.

12.11 Electrocardiogram

The screening ECG must be performed within the 28-day screening, also during the first visit of the 2nd cycle, before starting the treatment with Atezolizumab, and during the EoS visit in all participants. If medications known to prolong the QTcF interval are used while a patient is on study, then additional ECG monitoring should be performed as clinically indicated.

12.12 Physical Examination and Extra-medullary Leukemia Involvement

A complete physical examination will include the examination of general appearance, skin, neck (including thyroid), eyes, ears, nose, throat, lungs, heart, abdomen, back, lymph nodes, extremities, vascular, and neurological. Presence of extra-medullary leukemic involvement will be checked along with each physical examination as outlined above. Findings on physical examination consistent with extra-medullary leukemic involvement will be recorded (e.g., lymph nodes, liver and spleen size). With regards to lymph nodes, only those palpable lymph nodes should be considered to be CML related if leukemic blast infiltration has been confirmed via biopsy/histology or by technically adequate (not contaminated with peripheral blood) aspiration cytology. When extra-medullary involvement other than the spleen or liver is the only evidence of blast crisis, this finding must be confirmed by technically adequate (not contaminated with peripheral blood) aspiration cytology and /or biopsy (especially for isolated lymph nodes) and data entered into the extra-medullary involvement eCRF.

Information about the physical examination must be present in the source documentation at the study center and will be collected during the following visits:

- Screening
- During first therapy:
 - Day 1 of cycle 1 (before treatment).
 - Day 15 of cycle 1.
- During second therapy (before treatment):
 - Day 1 of cycle 2. Before the patient takes the bosutinib plus atezolizumab combination for first time.
 - Day 1 of cycles 4, 7, 10, and 13.
- During third therapy:
 - Day 1 of cycle 14. Before the patient takes bosutinib 400 mg/day in monotherapy, for the first time again for the treatment of CML.
 - Day 1 of cycles 17, 20 and 23.
 - At the End of Treatment: Day 29 (Last dose) of cycle 25.
 - At the End of Study, (visit EOS or follow up): 28 days after the last dose.

12.13 Eastern Cooperative Oncology Group (ECOG) Performance Status

ECOG performance status should be evaluated during each physical examination.

Table 19. ECOG Performance Status Scale

Description	Grade
Fully active, able to carry on all pre-disease activities without restriction.	0
Restricted in physically strenuous activity but ambulatory and able to carry out work of a light or sedentary nature e.g., light housework, office work.	1

Description	Grade
Ambulatory and capable of all self-care but unable to carry out any work activities. Up and about more than 50% of waking hours.	2
Capable of only limited self-care, confined to bed or chair more than 50% of waking hours.	3
Completely disabled. Cannot carry on any self-care. Totally confined to bed or chair.	4
Dead.	5

Information about ECOG must be recorded in the source documentation at the study center and will be collected on the following visits:

- Screening
- During first therapy (before treatment):
 - Day 1 of cycle 1 (visit 1/D1).
- During second therapy (before treatment):
 - Day 1 of cycle 2. Before the patient takes the bosutinib plus atezolizumab combination for first time.
 - Day 1 of cycles 4, 7, 10, and 13.
- During third therapy:
 - Day 1 of cycle 14. Before the patient takes bosutinib 400 mg/day in monotherapy, for the first time again for the treatment of CML.
 - Day 1 of cycles 17, 20 and 23.
 - At the End of Treatment: Day 29 (Last dose) of cycle 25.
 - At the End of Study, (visit EOS or follow up): 28 days after the last dose.

12.14 Blood Samples for BCR-ABL Molecular Response Assessment

MR will be assessed in all patients. Levels of BCR-ABL transcripts will be determined by real-time quantitative PCR (RT-qPCR) testing of peripheral blood and analyzed at a FTH designated central laboratory. The percent ratio of BCR-ABL transcripts versus control gene transcripts converted to IS will be calculated for each sample.

RT-qPCR will be done on:

- Screening
- During second therapy (before treatment):
 - Day 1 of cycle 2. Before the patient takes the bosutinib plus atezolizumab combination for first time.
 - Day 1 of cycles 4, 7, 10, and 13.
- During third therapy:
 - Day 1 of cycles 17, 20 and 23.
 - At the End of Treatment: Day 29 (Last dose) of cycle 25.

12.15 Laboratory Evaluations

Local laboratories will be used for analysis of hematology specimens collected and for analysis of biochemistry and serology specimens collected.

12.15.1 Complete Blood Count (CBC) With Differential

CBC with differential is defined as peripheral blood total white blood cell (WBC) count, hemoglobin, hematocrit, platelet count, red blood cell count, leucocytes, absolute neutrophil count (ANC), and WBC differential, reported individually for each cell type. Hematologic assessments must be obtained at:

- Screening
- During first therapy:
 - Day 1 of cycle 1 (before treatment).
 - Day 15 of cycle 1.
- During second therapy (before treatment):
 - Day 1 of cycle 2. Before the patient takes the bosutinib plus atezolizumab combination for first time.
 - Day 1 of cycles 4, 7, 10, and 13.
- During third therapy:
 - Day 1 of cycle 14. Before the patient takes bosutinib 400 mg/day in monotherapy, for the first time again for the treatment of CML.
 - Day 1 of cycles 17, 20 and 23.
 - At the End of Treatment: Day 29 (Last dose) of cycle 25.
 - At the End of Study, (visit EOS or follow up): 28 days after the last dose.

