9.1 Patient Screening

This study will be conducted on those naïve patients with chronic-phase Chronic Myeloid Leukemia (CP-CML) who meet the established selection criteria (see below). The patients that sign the IC and meet the selection criteria will be selected to enter the study.

Results of all screening evaluations must be reviewed by the Principal Investigator or his/her designee prior to the enrollment of a patient into the study to assure that all inclusion and none exclusion criteria have been satisfied.

All study patients must be thoroughly informed about all aspects of the study, including the study visit schedule and required assessments for informed consent. The written informed consent must be obtained prior to any screening evaluations. If a patient is unable to read, an impartial witness should be present during the entire informed consent discussion.

This is an open label clinical trial, and no randomization or blinding procedures are required.

The patients will be divided in two groups, with different start points, and will have three different therapy combinations during the study, which are described below. The first 10 patients included in the study will begin first. If at least 9 of these patients do not suffer DLTs during the first 2 cycles of the combined treatment (bosutinib 400 mg/day plus atezolizumab 840 mg every two weeks), the following 26 patients will be included, otherwise, the study will be terminated.

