9.3 Second Therapy

9.3.1 Group 1: The first 10 patients

Only for the first ten patients included in the study, atezolizumab will be introduced at a dose of 840 mg every two weeks combined with 400 mg/day of bosutinib for 2 cycles (8 weeks). These patients will be closely monitored for safety issues.

If dose-limiting toxicities (DLTs) appear in 2 or more patients the study will end.

A DLT would include either of the following adverse events that occurred during bosutinib therapy in combination with atezolizumab, if it is considered at least possibly related to bosutinib and/or atezolizumab:

- Grade 4 neutropenia (<500/ μ l) persisting for > 7 day duration or Grade 4 white cell count decrease for >7 day duration (<1000/ μ l).
- Febrile neutropenia (ANC<1000/ μ l and fever \geq 38.5°C).

- Grade 4 thrombocytopenia > 48 hour duration or with bleeding requiring platelet transfusion.
- Any Grade 3 or 4 clinically evident non-hematological toxicity.
- Any ≥Grade 3 toxicity that requires >14 days to resolve (to ≤Grade 1 despite optimal medical therapy).

DLTs will be graded according to the NCI CTCAE, v5.0.

If no relevant safety issue, regarding the combination is detected the study will continue.

These initial 10 patients will cross-over from bosutinib 400 mg/day plus atezolizumab 840 mg every 2 weeks to bosutinib 400 mg/day plus atezolizumab 1680 mg every 4 weeks for 10 cycles (40 weeks).

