11.6.1.2 Hematologic Treatment-Related Toxicity

Dose reductions are recommended for severe or persistent neutropenia and thrombocytopenia. The management of hematologic treatment-related toxicities is summarized in Table 2.

Table 2. Hematologic Treatment-Related Toxicity

Adverse Event	Action
Grade 1	Current dose level
Grade 2	Current dose level
Grade 3 ^a	Withhold treatment: If recovered to Grade ≤ 2 within 2 weeks of treatment hold: re-introduce study drug at same dose. If recovered within 4 weeks of treatment hold: reduce study drug by 1 dose level. At subsequent occurrences of Grade 3 toxicity, dose must be reduced upon recovery to Grade ≤ 2 . If recovery takes longer than 4 weeks, the Investigator should contact the Sponsor to determine if the patient may continue on treatment.
Grade 4 ^a	Withhold treatment. Investigator and Sponsor to review to determine if patient may continue on treatment with appropriate dose reduction. 
a. For patients requiring dose reduction due to toxicity, who have been free of the toxicity (Grade ≤ 1) for at least 1 month and are otherwise tolerating study drug, the Investigator may choose to re-escalate dose by 1 dose level back to starting dose

Subjects fulfilling criteria for dose escalation due to suboptimal response, but also exhibiting Grade 2 hematologic treatment related toxicity will be eligible for dose escalation; however, if hematologic toxicity increases to Grade 3 or 4 after dose escalation, the subject will be managed as per the instructions for Grade 3 or 4 hematological toxicities in Table 2.

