Vital Signs	X	X ⁽¹⁾	X ⁽¹⁾	X ⁽¹⁾	X ⁽¹⁾	X ⁽¹⁾	X ⁽¹⁾	X ⁽¹⁾	X ⁽¹⁾	X ⁽¹⁾	X ⁽¹⁾	X ⁽¹⁾	X ⁽¹⁾	X ⁽¹⁾	X ⁽¹⁾	X ⁽¹⁾	
Weight	X	X ⁽¹⁾		X ⁽¹⁾				X ⁽¹⁾									
Height	X																
12-Lead Electrocardiogram	X			X ⁽¹⁾	As clinically indicated												
Physical Examination and Extra-medullary Leukemia Involvement	X	X ⁽¹⁾	X ⁽¹⁾	X ⁽¹⁾				X ⁽¹⁾				X ⁽¹⁾		X ⁽¹⁾		X ⁽¹⁾	
ECOG	X	X ⁽¹⁾		X ⁽¹⁾				X ⁽¹⁾									
Blood Sample for BCR-ABL1 Assessment	X			X ⁽¹⁾				X ⁽¹⁾									

1 st Group of Patients (The 10 First Patients)		1 st Therapy		2 nd Therapy														
VISIT	Visit 0	Visit 1	Visit 2	Visit 3	Visit 4	Visit 5	Visit 6	Visit 7	Visit 8	Visit 9	Visit 10	Visit 11	Visit 12	Visit 13	Visit 14	Visit 15	Visit 16	
Cycle	Screening / Baseline	Cycle 1		Cycle 2		Cycle 3		Cycle 4	Cycle 5	Cycle 6	Cycle 7	Cycle 8	Cycle 9	Cycle 10	Cycle 11	Cycle 12	Cycle 13	
Day within Cycle (Visit Window ± 3 Days)	-28/-1	1	15	1	15	1	15	1	1	1	1	1	1	1	1	1	1	
Consecutive Days in the Study (D)	-28/-1	D1	D15	D29	D43	D57	D71	D85	D113	D141	D169	D197	D225	D253	D281	D309	D337	
Complete Blood Count with Differential	X	X ⁽¹⁾	X ⁽¹⁾	X ⁽¹⁾				X ⁽¹⁾			X ⁽¹⁾			X ⁽¹⁾			X ⁽¹⁾	
Chemistry	X ⁽²⁾	X ⁽¹⁾		X ⁽¹⁾⁽²⁾				X ⁽¹⁾⁽²⁾			X ⁽¹⁾⁽²⁾			X ⁽¹⁾⁽²⁾			X ⁽¹⁾⁽²⁾	
Serology	X																	
Bone Marrow Aspirate and Cytogenetic, if no-CCyR	X							X			X			X			X	
Pregnancy Test		X		X		X		X	X	X	X	X	X	X	X	X	X	
Immunological Studies	X			X ⁽¹⁾													X ⁽¹⁾	
Adverse Events	Medical History	Continuous																
Concomitant Medications	Medical History	Continuous																
Dispensing or Return of Bosutinib		X ⁽⁴⁾						X			X			X			X	
Atezolizumab Administration				X	X	X	X	X	X	X	X	X	X	X	X	X	X	

(1): The tests will be performed before IMP dose administration.

(2): Determination of lipase and amylase levels included.

(3): If the patient achieves CCyR, the cytogenetic assessment is not necessary.

(4) Dispense only bosutinib treatment.

Table 15. Schedule of Assessments 3rd Therapy for the first 10 patients

1 st Group of Patients	3 rd Therapy					
VISIT	Visit 17	Visit 18	Visit 19	Visit 20	Visit 21 (EOT)	Visit 22 (EOS)
Cycle	Cycle 14	Cycle 17	Cycle 20	Cycle 23	Cycle 25	Follow-up
Day within Cycle (Visit Window ± 14 Days)	1	1	1	1	29	28 days after the last dose
Consecutive Days in the Study (D)	D365	D449	D533	D617	D700	D728
Vital Signs	X ⁽¹⁾	X	X	X	X	X
Weight	X ⁽¹⁾	X	X	X	X	X
12-Lead Electrocardiogram	As clinically indicated					X
Physical Examination and Extra-Medullary Leukemia Involvement	X ⁽¹⁾	X	X	X	X	X
ECOG	X ⁽¹⁾	X	X	X	X	X

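### Group 1 has no scheduled on-combination blood count or chemistry before D85 (D82 at the earliest), so silent laboratory DLTs in the eight-week go/no-go window depend on unscheduled tests or one late check

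*Protocol*

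**What the plan says.** **Decision rule.** Group 1 starts atezolizumab 840 mg on D29, with further infusions on D43, D57 and D71 (Protocol Table 14). Section 9.1 judges DLTs "during the first 2 cycles of the combined treatment". Section 9.3.1 adds: "If dose-limiting toxicities (DLTs) appear in 2 or more patients the study will end". Otherwise the next 26 patients are enrolled.

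**Criteria that need blood tests (9.3.1).** Three routes to a DLT can be silent:
- grade 4 neutropenia lasting more than 7 days, or "Grade 4 white cell count decrease for >7 day duration";
- "Grade 4 thrombocytopenia > 48 hour duration or with bleeding requiring platelet transfusion", where the 48-hour arm is the silent one;
- grade 3 or worse "toxicity that requires >14 days to resolve".

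Silent chemistry can count only by the third route, because the other non-hematological criterion requires the toxicity to be clinically evident.

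**Schedule.** Section 12.15.1 lists counts on day 1 of cycle 2, before the first combination dose, and then on "Day 1 of cycles 4, 7, 10, and 13". Section 12.15.2 lists the same second-therapy days for chemistry. Table 14 agrees. Its row "Complete Blood Count with Differential" and its chemistry row are marked at D29 and D85, both with the pre-dose footnote, and are blank at D43, D57 and D71.

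**Dosing rules that use laboratory results.** For atezolizumab these are the general grade 3 hold in 11.6.2, Table 4 (hepatic) and Table 9 (amylase and lipase). For bosutinib they are Table 1 (transaminases) and Table 2, which 11.6.1.2 introduces with "Dose reductions are recommended for severe or persistent neutropenia and thrombocytopenia".

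**The concern.** The trial's main early safety decision rests on a DLT count over eight weeks, and part of the DLT definition can be applied only if blood is drawn in those weeks. None is scheduled. An asymptomatic grade 4 count or grade 3 chemistry value that starts after D29 and resolves before D85 leaves no scheduled trace. The error has one direction: a missed event lowers the DLT count and favours enrolling 26 more patients.

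The gap also affects patients directly. Three infusions each (D43, D57, D71) are given without a scheduled on-combination result against which to apply the atezolizumab hold rules, and daily bosutinib continues without one for Tables 1 and 2. That part of the concern needs no assumption about DLT rates. The contrast with the lead-in is notable: bosutinib alone has counts on D1 and D15, and again on D29 before the combination starts. The new combination then has none for eight weeks.

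**Working it through.** **1. Reproduce the plan's days.** With 28-day cycles, day 1 of cycle k is D = 1 + 28(k - 1). Cycle 2 gives D29, cycle 3 D57 and cycle 4 D85, as in Table 14. The window runs from D29 to 29 + 56 - 1 = D84. With the 3-day allowance, the D85 draw falls on D82-88. Scheduled draws after the first combination dose and before the D85 visit: 0.

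The plan states no error rates for the 2-of-10 rule. The only calculation in 15.5, 36 x 0.85 = 30.6, reproduces its 30-31 patients but does not bear on this point.

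**2. The rule itself.** P(stop) = 1 - (1 - p)^10 - 10p(1 - p)^9, where p is the per-patient probability of a counted DLT. This gives 26.4% at p = 0.10 and 59.3% at p = 0.19.

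**3. Assumptions (none is in the documents).**
- Onset of a silent event is uniform over the 56 days, and the event lasts L days.
- No unscheduled test finds it first.
- A 10% rate of clinical DLTs, always seen, and independently a laboratory-only rate q = 10%.
- An abnormal draw is repeated after g days (2 for platelets, 7 for neutrophils or white cells, 14 for the resolution criterion). The event counts only if the repeat is still abnormal.
- A D85 finding confirmed afterwards counts.

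Both schedules are given the same repeat rule, so the comparison isolates the added draws.

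**4. Share of silent events proved (s).** With D85 only, s = (L - g)/56. With D43, D57, D71 and D85, s = min(1, 4(L - g)/56).

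**5. Chance of stopping.** p = 1 - (1 - 0.10)(1 - q s), put into step 2. Example, 14-day neutropenia: D85 only gives p = 1 - 0.9 x (1 - 0.10 x 0.125) = 0.111 and P(stop) = 30.8%. Four draws give p = 1 - 0.9 x (1 - 0.10 x 0.5) = 0.145 and P(stop) = 43.7%.

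| Silent event | L | g | s, D85 only | s, four draws | P(stop), D85 only | P(stop), four draws |
|---|---|---|---|---|---|---|
| Grade 4 platelets | 3 | 2 | 1.8% | 7.1% | 27.0% | 28.9% |
| Grade 4 neutrophils or white cells | 8 | 7 | 1.8% | 7.1% | 27.0% | 28.9% |
| Grade 4 neutrophils or white cells | 14 | 7 | 12.5% | 50% | 30.8% | 43.7% |
| Grade 3 or worse, slow to resolve | 15 | 14 | 1.8% | 7.1% | 27.0% | 28.9% |
| Grade 3 or worse, slow to resolve | 28 | 14 | 25% | 100% | 35.1% | 59.3% |

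**6. Range over q.** For the neutrophil rows, q = 5% gives 26.7% to 27.6% (8-day) and 28.6% to 35.1% (14-day). q = 20% gives 27.6% to 31.4% and 35.1% to 59.3%. The gain is thus about 1 to 4 points for 8-day events and 6.5 to 24 points for 14-day events.

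**7. Contact without proof of duration.** A draw meets an episode at all with probability L/56 now and min(1, 4L/56) with the added draws: 14% against 57% for 8 days, 50% against 100% for 28 days, and 75% against 100% for 42 days. Meeting an episode once does not establish a duration-based DLT.

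**8. Limit of the model.** The last two table rows use one length for both time at grade 3 or worse and time to resolution. The criterion needs grade 3 first and only non-resolution afterwards, and it presupposes optimal medical therapy, so it is unclear whether an unseen, untreated value would qualify. Those rows are rough.

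**The case against.** The case on the other side limits the consequence, not the schedule fact.

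- **Other detection exists.** Adverse events are recorded continuously (12.19), patients attend every two weeks, 9.3.1 promises close monitoring, and 11.6.2.2 says liver function is followed throughout, with immediate tests for certain symptoms. None of these names a test day, and the immediate tests are for symptomatic patients. But a reader might infer that DLTs in the window cannot be detected, and the documents do not support that. Clinically evident DLTs remain visible, and unscheduled tests are allowed.
- **D85 has value.** It precedes the first 1680 mg dose, and a toxicity persisting to D85 would be seen. Later DLTs on 1680 mg still trigger a change of schedule (9.3.2, 11.5), though they do not end the study.
- **Follow-up rules exist once a value is known.** Table 9 requires amylase and lipase every other day at grade 3-4, Table 4 asks for more frequent liver tests at grade 2, and Table 2 implies follow-up counts. The gap is first detection, plus the absence of exact repeat times for grade 4 counts.
- **Larger effects are tempting.** If every episode met by a draw counted, the chance of stopping would move from 31% to 46% (8-day) or 36% to 59% (15-day). That ignores the duration requirements in 9.3.1, so those shifts should not be quoted as the effect.
- **Table 2 is not an infusion rule.** It sits under the bosutinib dose steps. The infusion argument rests on 11.6.2, Table 4 and Table 9.
- **Stopping more often is not shown to be right.** The plan states no acceptable DLT rate. At the example's full rate of 1 - 0.9 x 0.9 = 19%, nothing says that the study ought to end.

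All of this stands, and it reduces the claim to weak and discretionary detection of silent events.

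**Conclusion.** The concern holds in limited form. That the D29-84 window has no scheduled on-combination blood test, apart from a D85 draw taken on D82-84, is certain: two text sections and Table 14 agree. It follows that the silent laboratory DLT criteria cannot be applied reliably in that window, that misses favour no DLT, and that the atezolizumab and bosutinib hold rules lack a scheduled result for eight weeks.

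The effect on the go/no-go is uncertain. Under the stated assumptions it is about 2 points for events that barely exceed their duration limit, and 13 to 24 points for 14-day neutropenia or a 28-day grade 3 or worse event. All gains are upper bounds, because they assume no unscheduled testing. They measure detection and do not show a better decision. The dosing argument and the low cost are enough to make this a should-fix.

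**What to change.** Amend 12.15.1, 12.15.2 and Table 14 for Group 1:
- Draw the existing count and chemistry panel, with amylase and lipase, before infusion on D43, D57 and D71, and review the results before dosing.
- State that the pre-dose D85 draw counts in the DLT evaluation.
- Repeat grade 4 platelets after 48 hours, and grade 4 neutrophils or white cells after 7 days.
- Repeat other grade 3 or worse chemistry at least every two weeks until grade 1 or better, keeping any more frequent monitoring already required (Table 9 for amylase and lipase, Table 4 for liver tests).

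Cost: 10 patients x 3 visits = about 30 local draws at visits already attended, occasional repeat visits, and one amendment. An abnormal D85 value could delay the go/no-go by 2 to 14 days while its duration is confirmed. Short cytopenias between draws can still be missed, and the amendment should say so.
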